6. GENERAL ANALYSIS DEFINITIONS

6.1 TREATMENTS

For reporting purposes, all patients will be classified into one of the following treatment groups as determined by random treatment assignment at the start of 1293.10:

Sort order	Treatment	Long label	Short label
01	B	BI 655064 120mg	BI 120mg
02	C	BI 655064 180mg	BI 180mg
03	D	BI 655064 240mg	BI 240mg
04	A	Placebo	Placebo

These will be the default labels and sort order for reporting the treatment groups.

The following study periods based on actual start and stop dates of study treatment administration are defined:

Treatment: start date of randomised to double-blind medication in 1293.10 to date of last dose in 1293.13

Follow-up: day after the last dose of randomised double-blind medication in 1293.13 through trial completion and after trial completion

Rules for assigning AEs/laboratory data to the study periods are as follows.

AEs/laboratory data will be assigned to the treatment period if they occur/samples were taken after the first injection of study medication to the date of last administration of study medication plus 50 days.

Adverse events with onset on or after the 51st day after the last administration of trial medication will be considered 'Follow-up' events.

Laboratory data on or after the 51st day after the last administration of trial medication will be considered 'Follow-up' data.

6.2 IMPORTANT PROTOCOL DEVIATIONS

The following table defines the different categories of important protocol deviations (iPDs). The final column indicates which iPDs will be used to exclude patients from the different patient analysis sets.

Patients with iPDs will be documented. The following list of iPDs will be used; note that this is a working list and may not be finalised until the final Report Planning Meeting (RPM) prior to database lock.

Proprietary confidential information © 2021 Boehringer Ingelheim International GmbH or one or more of its affiliated companies

Excluded from ‘None’ denotes a safety iPD.

Table 6.2: 1 Handling of iPDs

Category/ Code	Description	Example/Comment	Excluded from
A	Entrance criteria not met -	automatic PVs	
A1.1	Patient must have a CRR or a PRR or proteinuria \leq 1g/d (or UP/UC \leq 1)	Note: This can be at Week 46 or Week 52 of 1293.10.	PPS
A1.2	Women of childbearing potential must be ready and able to use two reliable methods of birth control simultaneously; one must be highly effective. Sexually active men must be ready to use condoms during & following treatment with MMF		None
A2.1	Clinically important acute or chronic infections including but not limited to HIV, hepatitis B or C.		PPS
A2.2	Estimated glomerular filtration rate (eGFR) $<$ 30 ml/min/1.73m ² at screening (using CKD-EPI formula).		
A2.3	The use of any restricted medications (see CTP) or any drug considered likely to interfere with the safe conduct of the trial.		
B	Informed consent		
B1	Informed consent not available/not done	Informed consent date missing (automatic PV)	All
B2	Informed consent too late	Informed consent date $<$ actual consent date $>$ was after Visit 1 date $<$ Visit 1 date $>$ (automatic PV)	None
C	Trial medication and randomization		
C1	Randomization not followed	Patient was not assigned to the treatment group specified in BI's randomization schedule. (to be checked at time of DBL).	None (TBD at MQRM/BRPM)

Proprietary confidential information © 2021 Boehringer Ingelheim International GmbH or one or more of its affiliated companies

Table 6.2: 1 (continued) Handling of iPDs

	C2	Wrong dosage schedule	(1)Medication number dispensed was not the medication number assigned OR (2)syringes used in the wrong order	PPS/ (TBD at MQRM/BRPM)
	C3	Non-compliance with study medication	Any evidence of gross non-compliance. (Patient meets the non-compliance criteria in Section 5.4) (manual or automatic PV)	PPS/ (TBD at MQRM/BRPM)
	C4	Medication code broken inappropriately	Medication code broken inappropriately - reason for medication code break <reason> (manual PV)	PPS
D		Concomitant medication		
	D1	Prohibited medication use (as described in CTP, section 4).	
 • Abatacept or Cyclophosphamide during treatment period • Cyclosporine / Tacrolimus / Mizoribine during treatment period (permitted during follow up per investigator's decision) • Belimumab or other "anti- BLYS" or another investigational drug during treatment period • Biologic B-cell depleting therapy (e.g. anti-CD20) during treatment period • IV glucocorticoids during treatment period (Automatic & Manual iPVs)	PPS/ (TBD at MQRM/BRPM)
	D2	Non-permitted oral steroid use (as described in CTP, section 4.2.1)	
 • Patients with a CRR or proteinuria of <0.8g/d at the end of 1293.10 should start steroid tapering immediately at Visit 1. If necessary, patients may remain on a certain level of steroids due to other symptoms of SLE based on investigator's judgement. Although the tapering schedule will allow some flexibility, however steroids should be stopped at 3 months (Week 12) after randomisation. If this this not possible due to the patient's medical condition, the patient can stay on the lowest possible dose with the best benefit. • Patients with proteinuria of ≥0.8g/d at the end of 1293.10 should taper steroids down to ≤7.5mg/d at week 26 and then to ≤5mg/d at week 52. 	PPS/ (TBD at MQRM/BRPM)

[figure not shown]
Proprietary confidential information © 2021 Boehringer Ingelheim International GmbH or one or more of its affiliated companies

Table 6.2: 1 (continued) Handling of iPDs

	D4	Non-permitted AZA dose	AZA is allowed at a stable dose of 2mg/kg/day. (In case of intolerance or the body weight <50kg, dose may be reduced to 1mg/kg/day or the dosage should be rounded to the nearest 50mg. In regions where only a fixed single dosage is available on the market, the rounding should be done according to the investigators judgment, not exceeding 2mg/kg/day.)	PPS/ (TBD at MQRM/ BRPM)
	D5	Non-stable dose of ACE inhibitors or ARBs	ACE inhibitors or ARBs allowed at stable dose.	PPS/ (TBD at MQRM/ BRPM)
G		Trial specific		
	G1	Failure to remove patient from therapy (=study medication)	As described in CTP section 3.3.4.1	PPS/ (TBD at MQRM/ BRPM)
Z		Other		
	Z1	Other iPVs affecting efficacy and possibly safety		PPS/ (TBD at MQRM/ BRPM)
	Z2	Other iPVs affecting safety only		None

6.3 SUBJECT SETS ANALYSED

- **Randomised set:**
This patient set includes all randomised patients, whether treated or not.
- **Treated set:**
This patient set includes all patients who were dispensed study medication and were documented to have taken at least one dose of investigational treatment.
- **Intent to treat (ITT) set:**
This patient set includes all patients from the treated set who have a baseline (or screening) proteinuria (spot urine can be a used if patient does not have 24-hour collections) and baseline or screening eGFR

[figure not shown]
The Per protocol set (PPS) was dropped with the second CTP amendment.

Proprietary confidential information © 2021 Boehringer Ingelheim International GmbH or one or more of its affiliated companies

Table 6.3: 1 Subject sets analysed

Class of endpoint	Patient set		
	Treated set	ITT	
Primary endpoint: CRR at week 52		X	
Secondary endpoints		X	
Safety endpoints	X		
Demographic/baseline endpoints	X		

Note that the number of patients with available data may differ across endpoints. For details, see [Section 6.6](#) “Handling of missing data”.

6.5 POOLING OF CENTRES

This section is not applicable because centre/country is not included in the statistical model.

6.6 HANDLING OF MISSING DATA AND OUTLIERS

6.6.1 Primary, secondary [REDACTED] endpoints

As CRR is defined based on UP (and UP/UC) from the two 24h urine collections and eGFR calculated from serum creatinine, rules for derivation of CRR when one or both of the urine samples and/or the serum sample is missing are specified below.

If one 24h urine collection is missing at any time point, then calculations should be based on the available 24h collection at that time point. If one 24h urine collection at any time point is suspected to be incomplete (<500mL/day or time of collection is <19.5 hours) or otherwise not evaluable, then calculations should be based on the unaffected collection at that time point.

Note that the restrictions on volume and duration of collection do not apply to the UP/UC derivation as the adjustment using UC is thought to compensate for incomplete collections.

The following rule was applied to the baseline of 1293.10. If both 24h urine collections at baseline are missing, suspected to be incomplete or not evaluable, then UP/UC from the spot urine at baseline should be used to impute baseline UP (or UP/UC) from a 24h collection.

Proprietary confidential information © 2021 Boehringer Ingelheim International GmbH or one or more of its affiliated companies

Handling missing data for patients who do not prematurely stop trial medication

If a patient does not have 24h urine collections at week 52, then UP from a 24h collection will be imputed as follows:

- For the week 52 UP, use the mean of UP/UC from the spot urines at weeks 42 and 52

UP/UC from two weeks are used to get a more stable estimate of UP as it is generally accepted that estimates from the spot urines are not as reliable as estimates from the 24h collections.

For the derivation of CRR using UP/UC from the 24h collection, averages of the two weeks as described above will also be used to impute missing UP/UC from the 24h collection.

For the derivation of CRR using UP/UC from the spot urine, the imputation would be as follows: If UP/UC from the spot urine is missing at week 26, then use week 18. If UP/UC from the spot is missing at 52; use 42.

If no serum creatinine value (to determine eGFR) was available at baseline in 1293.10, then it was imputed using the value at the screening visit. If no serum creatinine value is available at week 26 or week 52 in 1293.13, then it will be imputed using the value at week 18 or week 42, respectively.

For secondary and further endpoints based on proteinuria and eGFR, the same imputation rules will be applied to derive response at weeks 26 and 52.

Definition/derivation of CRR for patients who prematurely stop trial medication (not applicable to unblinded Placebo patients who obtained BI approval to stop injections)

The CTP specified that as an imputation technique to deal with missing data, for the analysis of primary and CRR-related secondary endpoints, non-completers considered failure will be used. To determine if this was a reasonable approach, the trial team reviewed the patients who discontinued early, including review of reasons for early treatment discontinuation, AEs, concomitant meds, renal labs. The following handling rules better fit the circumstances around treatment discontinuation & were adopted.

- (1) If the details around the early discontinuation of trial medication indicated that the patient discontinued due to worsening renal function, had a renal flare or needed rescue medication, then CRR & PRR will be defined as ‘Non-responder’.
- (2) If there was no discernable worsening of renal function & the patient had a reasonable treatment duration, renal tests at the time of treatment discontinuation will be used to derive CRR & PRR.
- (3) If neither of the above applies and if at the time of discontinuation, the patient could have been considered a responder, then the patient was considered censored or non-evaluable. If the patient discontinued before Week 26, then both Week 26 & Week 52 are non-evaluable. If the patient discontinued after Week 26, then CRR & PRR were derived for Week 26 & Week 52 is non-evaluable.

Proprietary confidential information © 2021 Boehringer Ingelheim International GmbH or one or more of its affiliated companies

For patients who took study drug for < 42 weeks, continued to participate in the trial and have urine collections and serum creatinine determinations, their data will be displayed in a separate listing.

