2.1.3 Secondary endpoints

- Proportion of patients with CRR at week 52
- Proportion of patients with proteinuria <0.8g/d and without any renal flares at week 52.
- Proportion of patients with CRR at week 52 and sustained steroid reduction to ≤ 5 mg/d from week 26 to week 52.
- Proportion of patients experiencing at least one renal flare during 52 weeks.
- Time to first renal flare over the course of 52 weeks.
- Proportion of patients with confirmed CRR (defined as CRR at both week 42 and week 52 using UP/UC from spot urine)
- Change from baseline in SLEDAI at weeks 12, 26, 42 and 52.

Safety endpoints:

- Physical examination
- Vital signs
- Safety laboratory tests
- Electrocardiogram
- Adverse events (including drug-related AEs)
- Adverse events of special interest (AESI)
- Serious adverse events

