5.2.2 Secondary endpoints

The secondary endpoints were re-ordered in order of perceived importance as follows:

[figure not shown]
- Proportion of patients with confirmed CRR (defined as CRR at both week 42 and week 52 using UP/UC from spot urine) without renal flare
The endpoint, confirmed CRR, was introduced as a post hoc endpoint for 1293.10 where it proved to be a more sensitive endpoint as it was able to detect treatment effect in the presence of an unexpected large placebo response. With the requirement to demonstrate CRR at both time points, the placebo effect at Week 52 was reduced resulting in meaningful response rates for 180 mg and 240 mg BI655064.
- Proportion of patients with proteinuria <0.8g/d and without any renal flares at week 52.
- Proportion of patients with CRR at week 52 and sustained steroid reduction to ≤5 mg/d from week 26 to week 52.
- Proportion of patients experiencing at least one renal flare during 52 weeks
- Time to first renal flare over the course of 52 weeks.
- Proportion of patients with PRR without renal flare derived from UP 24h collection at Week 52.
Although not included in the list of endpoints in the CTP, PRR is defined in the CTR along with CRR as an assessment of renal response.
It is defined as at least 50% reduction of proteinuria from baseline and **either** eGFR within normal range at time of assessment or decrease of eGFR < 20% from baseline if eGFR below normal range at time of assessment.
- Change from baseline in SLEDAI at weeks 12, 26, 42 and 52.
- Proportion of patients with CRR at Week 52.
It was decided that CRR alone without consideration of whether a patient experienced a renal flare was not appropriate as the occurrence of a flare indicates the patient was not a responder. This endpoint will not be analysed.

Proprietary confidential information © 2021 Boehringer Ingelheim International GmbH or one or more of its affiliated companies

Proprietary confidential information © 2021 Boehringer Ingelheim International GmbH or one or more of its affiliated companies

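### For confirmed CRR, SAP 6.6.1 lets Week 42 values replace missing Week 52 values, so one visit can count as both

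*SAP*

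**What the plan says.** **Definition.** SAP 5.2.2 defines the endpoint as "confirmed CRR (defined as CRR at both week 42 and week 52 using UP/UC from spot urine) without renal flare". Protocol 2.1.3 has the same two-visit requirement on spot urine, without the flare condition.

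**Reason for two visits.** SAP 5.2.2 explains what the second visit achieved in 1293.10: "With the requirement to demonstrate CRR at both time points, the placebo effect at Week 52 was reduced".

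**Role.** SAP 5.2.2 puts confirmed CRR at the head of its secondary list, which is ranked by importance. SAP 7.5.2 gives it the logistic and sensitivity analyses of the primary endpoint and makes it the endpoint for subgroup work.

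**Missing values, patients who stay on medication (SAP 6.6.1).** For CRR derived from spot urine: "If UP/UC from the spot is missing at 52; use 42". For serum creatinine missing at Week 26 or Week 52: "it will be imputed using the value at week 18 or week 42, respectively". For secondary endpoints built on proteinuria and eGFR: "the same imputation rules will be applied to derive response at weeks 26 and 52". Neither 6.6.1 nor the visible text on confirmed CRR in 5.2.2, 7.4.2 and 7.5.2 makes an exception.

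**Early stoppers.** They follow three separate rules in 6.6.1. Under rule (3), "If the patient discontinued after Week 26, then CRR & PRR were derived for Week 26 & Week 52 is non-evaluable".

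**The concern.** For an endpoint read at one visit, filling from the adjacent visit is ordinary carry-forward. For an endpoint whose whole content is that the response was seen twice, the same fill is circular: the copied value cannot fail at Week 52 if it passed at Week 42. The second demonstration, which the SAP credits with lowering the placebo response, then does not take place for that patient.

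What is at stake is the meaning of a confirmed response in the leading secondary endpoint, in a trial with about 60 patients over four arms. The fill rules name Weeks 26 and 52 only, and none is shown for a missing Week 42 value. They read as written for single-visit CRR, so the effect on confirmed CRR may be unintended. As the text stands, a programmer would still apply it.

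**Working it through.** The plan states no figure on this point, so there is nothing to reproduce. The check is a trace of the rule, followed by its size under stated assumptions.

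**1. Trace of the rule (no flare, Week 42 values available)**

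| Week 42 | Week 52 | Under SAP 6.6.1 | Missing = not confirmed |
|---|---|---|---|
| CRR | CRR | confirmed | confirmed |
| CRR | not CRR | not confirmed | not confirmed |
| CRR | both values missing | **confirmed** | not confirmed |
| not CRR | any, or missing | not confirmed | not confirmed |

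Only the third row differs. If just one of spot UP/UC and creatinine is missing, the copied component passes automatically for a Week 42 responder, while the other is still a real Week 52 test. A Week 42 non-responder is never confirmed, whatever is filled in. So, against complete data, the copy can turn a true *not confirmed* into *confirmed* but never the reverse.

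**2. Size as a rate.** Assumed inputs, none of them in the documents: p = Week 42 CRR rate, 0.4 to 0.6; c = chance that a Week 42 responder is still CRR at Week 52, 0.7 to 0.9; m = share lacking both Week 52 values, 5% to 20%, unrelated to response.

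- Complete data: p × c
- SAP rule: p × [(1 − m) × c + m]
- Missing = not confirmed: p × c × (1 − m)
- SAP rule minus complete data: p × m × (1 − c). Smallest 0.4 × 0.05 × 0.1 = 0.2 points; largest 0.6 × 0.20 × 0.3 = 3.6 points.
- SAP rule minus not confirmed: p × m. Smallest 0.4 × 0.05 = 2 points; largest 0.6 × 0.20 = 12 points.

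With p = 0.5, c = 0.8 and m = 10%, complete data give 40.0%, the SAP rule 0.5 × (0.72 + 0.10) = 41.0%, and not confirmed 0.5 × 0.8 × 0.9 = 36.0%.

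**3. Size per patient.** Protocol 7.7 expects 60 patients. An equal split is assumed, 60/4 = 15, although SAP 7.4.1 says the arms are not balanced. One patient in the third row moves the arm's rate by 1/15 = 6.7 points relative to not confirmed (1/10 = 10.0 and 1/20 = 5.0 for arms of 10 and 20).

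To place the options, suppose that 6 of the other 14 patients are confirmed and that the affected patient would truly have been CRR at Week 52 with probability q = 0.6 to 0.8. The expected rate is (6 + q)/15 = 44.0% to 45.3%.

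- Carry-forward: 7/15 = 46.7%, an error of +2.7 to +1.3 points
- Not confirmed: 6/15 = 40.0%, an error of −4.0 to −5.3 points
- Non-evaluable: 6/14 = 42.9%, an error of −1.1 to −2.5 points

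**4. Can both values be missing in a patient still on drug?** Protocol Table 5.2.3:1 schedules chemistry and spot UP/UC at Week 52. Protocol 6.1 adds local-laboratory testing during pandemic restrictions, but only where possible. The same section ends participation when no safety laboratory sample can be taken for more than 12 weeks. Week 42 is Day 295 and Week 52 is Day 365, which is 70 days or 10 weeks, so a missed Week 52 sample alone does not trigger that rule. The situation is possible; its frequency is not stated.

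**The case against.** The strongest reply is that the set of patients is very narrow. They must stay on drug, respond at Week 42, have no flare and lack both values at a visit where both are scheduled. The trial is exploratory, with nominal p-values, and Protocol 7.5 leaves imputation detail to the SAP. All of this stands. It limits the weight of the point, but it does not remove the conflict between the rule and the endpoint's definition.

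A second reply is that *not confirmed* can sit further from the truth than the copy. The errors are q/n and (1 − q)/n, so the copy is closer whenever q exceeds 0.5, as in the examples above. That is correct arithmetic on assumed values of q. It answers a different question, however: what the unobserved Week 52 status probably was. The endpoint asks whether CRR was shown at both visits, and a copied value shows nothing at the second. Reporting carry-forward as the upper bound meets the objection.

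A reader might also infer a bias confined to the placebo arm. The early-stop rules are headed "not applicable to unblinded Placebo patients who obtained BI approval to stop injections", and the SAP does not say which missing-data rule covers those patients. The inference does not follow. The carry-forward block covers patients who stay on drug in every arm, and no text suggests that these placebo patients lack Week 52 samples. Protocol 6.2.3.3 invites even ordinary early stoppers to visits at Weeks 42 and 52 with creatinine and spot urine.

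**Conclusion.** The point holds as a conflict between a stated rule and the endpoint to which it is applied. Under SAP 6.6.1 a flare-free Week 42 responder with no Week 52 spot UP/UC or creatinine counts as confirmed on one visit. The effect on the rate is one-directional: nil or upward against complete data. One such patient is worth 6.7 points in an assumed 15-patient arm relative to *not confirmed*. Over the assumed ranges the excess over complete data is 0.2 to 3.6 points. The actual number of patients is not given and may be zero.

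Two stronger conclusions are not supported. First, no distortion of the comparison with placebo is shown: the documents give no per-arm counts, and with equal arm sizes, equal numbers affected and equal durability the shift cancels. Second, the two-visit problem does not reach the primary endpoint, which assesses CRR at Week 52 only. The same creatinine fill does feed eGFR for primary CRR, but there it is ordinary carry-forward.

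This should be fixed, because the endpoint leads the secondary list and carries the subgroup analyses, and the correction is small.

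**What to change.** Add to SAP 6.6.1 that Week 42 values are not carried forward to Week 52 when deriving confirmed CRR. As the main rule, a patient without the Week 52 spot UP/UC or creatinine needed to show CRR at Week 52 is *not confirmed*. Settle this before treatment information is released for analysis (SAP Section 8).

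Report three sensitivity analyses, with the number of affected patients per arm:

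- the current carry-forward, as the upper bound;
- *non-evaluable*, a category that rule (3) of 6.6.1 already uses for some early stoppers;
- a real Week 52 24-hour UP/UC where one exists. This stays a sensitivity analysis because the endpoint is defined on spot urine, and it does not help when creatinine is missing.

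The cost is a short paragraph, one changed derivation, three extra runs and a table of counts; no new data are needed. The downside is a possibly lower confirmed-CRR rate, by 6.7 points per affected patient in an assumed arm of 15, and a main analysis that errs low if most Week 42 responders hold their response.

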7.5 HANDLING OF MISSING DATA

As an imputation technique to deal with missing data in this study, for the analysis of primary and CRR-related secondary endpoints, non-completers considered failure will be used. Further details on the imputation approaches will be specified in the TSAP.

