Section to be changed		6.2.1 Baseline (group 1)
Description of change		1. Adding a description of the timepoint when the roll over decision can be made 2. Adding a wording for cases when the interruption between the trial is longer than 7 days. 3. replace randomization by enrollment
Rationale for change		1. To clarify that the latest timepoint for roll over decision can also be EOT of 1293.10 2. To clarify that in case of longer interruption certain lab parameters shall be taken as baseline for 1293-0013 3. To adapt to group 1 (with no randomization)
Section to be changed		6.2.2. Treatment period
Description of change		1. Removing reference to group 2 2. Adding a wording on treatment interruptions
Rationale for change		1. Group 2 was cancelled 2. To clarify that the CTL shall be informed about longer treatment interruptions.
Section to be changed		6.2.3.3. Additional follow-up for prematurely discontinued patients
Description of change		Adding a wording regarding follow up visit intervals
Rationale for change		To clarify when early discontinued patients shall come for follow up visits
Section to be changed		7.1 Statical design - model

Description of change		Modified design description to highlight important features of the Group 1-only trial
Rationale for change		Group 2 was cancelled
Section to be changed		7.2 Null and Alternative Hypotheses
Description of change		Further description/justification of statistical approach added.
Rationale for change		To more clearly describe how the statistical testing addresses the trial objectives.
Section to be changed		7.3. Planned analysis
Description of change		1. Analyses will incorporate data from 1293.10. 2. Baseline for 1293-0013 is defined as the baseline from 1293.10 unless otherwise indicated. 3. Baseline characteristics for patients who enter 1293-0013 (Group 1) will be compared to baseline characteristics for the treated population of 1293.10. 4. Population data set defined as ITT.
Rationale for change		1 & 2. With cancellation of Group 2, the analysis focus can be the long term (two-year) efficacy and safety assessment for the Group 1 patients. 3. Any relevant shifts in baseline characteristics could affect interpretation of results & should be noted. 4. Approach will be to consider discontinued patients as failures & include in analysis of the primary endpoint.
Section to be changed		7.3.1 Primary endpoint analysis

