4. CHANGES IN THE PLANNED ANALYSIS OF THE STUDY

With Amendment #2 to the CTP (21-Dec-2020), Group 2 was cancelled. Group 2 was to be a cohort of patients who achieved a meaningful response to induction treatment outside of 1293.10. With all patients in 1293.13 now coming from trial 1293.10 (Group 1), the sole focus in 1293.13 can be long-term (now 2-year) assessment of their induction and continued maintenance therapy in 1293.13. Efficacy and safety tables and figures will include data from 1293.10 for assessment of BI655064 doses versus placebo over this 2-year treatment period.

Amendment #2 describes the unblinding of treatment codes for 29 patients (20 on treatment and 9 in follow-up) in the trial on 20-Oct-2020. At that time, the investigator was asked to discuss with the patient their treatment options and continued participation in 1293.13. It is not expected that this partial unblinding introduced meaningful reporting bias. The primary endpoint and most of the secondary endpoints are derived from laboratory measurements. With respect to the SLEDAI, most domains are lab-based and other domains are examination findings. No analyses to address potential bias are planned.

The CTP list of secondary and further endpoints was reviewed (prior to release of treatment codes) resulting in some additions and a few deletions essentially driven by learnings from the 1293.10 trial. [Section 5.2](#) lists the secondary endpoints noting the addition of one endpoint (proportion of patients with partial renal response (PRR) without renal flare) inadvertently left off the CTP list of secondary endpoints (but specified in another section) and one deletion with explanation for the deletion (proportion of patients with CRR at Week 52). [REDACTED]

Important Protocol Deviations (iPDs) were updated during trial conduct to reflect learnings and input from Key Opinion Leaders (KOLs). The Per protocol set (PPS) was dropped with the second CTP amendment.

Sensitivity, subgroup and exploratory analyses added to the TSAP for the primary endpoint are listed in [Sections 7.4.2](#). Sensitivity, subgroup and exploratory analyses were also added to the TSAP for an important secondary endpoint; these are listed in [Sections 7.5.2](#).

The biomarker analysis will be outlined outside of this TSAP.

[REDACTED]

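### For stoppers without renal worsening, flare or rescue, SAP 6.6.1 replaces the protocol's failure rule with rules that leave outcomes open, and no protocol-rule result is planned

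*SAP*

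**What the plan says.** **Protocol.** Section 7.5 states that "for the analysis of primary and CRR-related secondary endpoints, non-completers considered failure will be used" and leaves further imputation details to the TSAP. The Global Amendment 2 rationale for the current section 7.3 agrees: "Approach will be to consider discontinued patients as failures & include in analysis of the primary endpoint". Section 4.2.1 separately treats patients given higher steroids or rescue therapy for worsening or flare as treatment failures in the analysis.

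**SAP 6.6.1.** It restates the protocol rule. It then reports that the trial team reviewed early discontinuers (reasons, AEs, concomitant medication, renal labs) and concludes: "The following handling rules better fit the circumstances around treatment discontinuation & were adopted". In short:

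- Rule 1: stopped for worsening renal function, had a flare or needed rescue. Non-responder.
- Rule 2: "there was no discernable worsening of renal function & the patient had a reasonable treatment duration". Renal tests at the stop decide CRR and PRR.
- Rule 3: neither of these applies, and "if at the time of discontinuation, the patient could have been considered a responder, then the patient was considered censored or non-evaluable".
- The heading adds that the rules are "not applicable to unblinded Placebo patients who obtained BI approval to stop injections".
- Patients with under 42 weeks on drug who stayed in the trial and have renal data appear in a separate listing.

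**Elsewhere in the SAP.** The sensitivity analyses of the primary endpoint in 7.4.2 are by race and by screening proteinuria only. The readable text of section 4 does not list this change. Section 7 takes percentages by default over all patients in the set, with or without values. Section 7.4.1 adopts a two-sided cut-off of 0.20 for pairwise comparisons.

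**The concern.** Protocol 7.5 lets the TSAP add detail, but turning some protocol failures into responders or non-evaluable patients changes the rule. The new rules were also written after individual stoppers' outcomes had been seen. Three things then matter.

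1. Two analysts could derive different primary results from the same data, because key terms have no numbers and some cases have no outcome.
2. No table will show the result under the protocol rule, so a reader of the report cannot see how much the change contributes.
3. For patients unblinded on 20 Oct 2020, handling depends in part on known arm, because the exemption names placebo only.

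The analysis is exploratory with nominal p-values. Still, Protocol 3.2 intends this trial, together with 1293.10, to support the choice of dose regimens for Phase III, and arms are small enough for a few patients to move a comparison across 0.20.

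**Working it through.** The plan gives no figure to reproduce: Protocol 7.7 estimates 60 patients and states that there is no power calculation.

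**Step 1. Follow a stopper through the rules**

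| Stopper | Protocol 7.5 | SAP 6.6.1 |
|---|---|---|
| Worsening, flare or rescue | Failure | Non-responder (rule 1) |
| No worsening, in response, duration judged reasonable | Failure | Responder (rule 2) |
| No worsening, in response, duration judged too short | Failure | Non-evaluable (rule 3) |
| No worsening, not in response, duration judged reasonable | Failure | Non-responder (rule 2) |
| No worsening, not in response, duration judged too short | Failure | No rule applies |
| Unblinded placebo patient with approval to stop | Failure, if a stopper counts as a non-completer | Exempt; no substitute rule stated |

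- Rows 2 and 3 differ only in an undefined duration. Week 26 in rule 3 decides which visits become non-evaluable, and 42 weeks governs the listing; neither is given as the duration threshold. Worsening has no numerical limit either.
- CRR and PRR do have numerical limits (Protocol 5.1.1, SAP 5.1 and 5.2.2). What rule 3 leaves open is which of them, on which sample, makes a patient a possible responder.
- For row 5, non-responder is the natural reading, but it is not stated.
- For row 6, the rules under "Handling missing data for patients who do not prematurely stop trial medication" may be intended, but the SAP does not say so. Unblinded BI 655064 patients who stop have no corresponding provision.

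**Step 2. Denominator under rule 3.** Calling a patient censored or non-evaluable suggests exclusion, and a logistic model drops a missing outcome. The SAP 7 default keeps the patient in the percentage. SAP 6.3 refers the reader to 6.6, which does not decide it.

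**Step 3. Timing and blinding.** Protocol 3.2 and 4.1.5.1 report 29 patients unblinded on 20 Oct 2020 (20 on treatment, 9 in follow-up). SAP version 2 is dated 17 Jun 2021. SAP 4 says: "The CTP list of secondary and further endpoints was reviewed (prior to release of treatment codes", and that statement concerns endpoints. No date or blinding statement is given for the stopper review. As 20/60 = 33%, the 20 on treatment are a third of the planned number, and the exemption can concern only the placebo patients among them.

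**Step 4. Size.** Arm sizes, stopper counts and response rates are not in the documents. Assume 60/4 = 15 per arm and, under the protocol rule, 8 responders on one BI 655064 dose and 5 on placebo. One patient is worth 1/15 = 6.7 points. The p-values are two-sided Barnard tests, one of the methods in SAP 7.4.1.

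| Case | BI v placebo | Difference (points) | p |
|---|---|---|---|
| Protocol rule | 8/15 v 5/15 | +20 | 0.32 |
| Rule 2, one BI stopper becomes responder | 9/15 v 5/15 | +27 | 0.23 |
| Rule 2, two BI stoppers | 10/15 v 5/15 | +33 | 0.099 |
| Rule 2, two placebo stoppers | 8/15 v 7/15 | +7 | 0.86 |
| Rule 2, two in each arm | 10/15 v 7/15 | +20 | 0.33 |
| Rule 2, three in each arm | 11/15 v 8/15 | +20 | 0.30 |
| Rule 3, three BI stoppers, kept in denominator | 8/15 v 5/15 | +20 | 0.32 |
| Rule 3, three BI stoppers, excluded | 8/12 v 5/15 | +33 | 0.099 |

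One reclassification does not cross 0.20 here; two on one side do. The denominator choice alone can also cross it. Equal reclassification changes little, and reclassification on placebo shrinks the difference.

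**The case against.** The strongest defence is that the change is open and clinically reasoned. SAP 6.6.1 states the old rule, explains the review and gives the new rules; Protocol 7.5 foresaw further detail in the TSAP. Rule 1 keeps failure where the disease got worse, in line with Protocol 4.2.1. The exemption has a plausible rationale, since stopping placebo removes no active drug. Individual data will be listed, including a specific listing for stoppers with under 42 weeks on drug. The trial is exploratory, and SAP 7.4.1 itself warns of inherent biases.

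Most of this stands, and it limits the point to stoppers outside rule 1. It does not supply the missing thresholds, an outcome for every stopper, the denominator, or a tabulated result under the protocol rule. The rationale for the exemption is a reader's inference; the SAP states none.

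Two stronger readings are tempting, and the documents support neither.

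- *The rules were chosen with knowledge of arm.* Some codes were known before SAP version 2, but the review is undated. Protocol 4.1.5.1 keeps staff conducting the trial blinded for patients not unblinded, although a limited number of sponsor personnel could be unblinded and bioanalytics receives codes before last patient out. The gap is one of reporting.
- *The rules favour BI 655064.* Step 4 shows movement either way. The protocol rule can itself favour BI 655064 by failing placebo patients who stopped with approval.

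**Conclusion.** The point holds for stoppers outside rule 1 and should be fixed. SAP 6.6.1 departs from the protocol's failure rule, its replacement is not fully reproducible, and no protocol-rule result is planned beside it.

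The textual findings rest on the readable SAP; section 4 contains redactions, but the sensitivity section 7.4.2 is readable. The size is illustrative only: it assumes four equal arms of 15, although SAP 7.4.1 says the groups are unbalanced, it assumes all counts, and it covers the Barnard comparison but not the logistic or CMH analyses. On those assumptions, two one-sided reclassifications or the rule 3 denominator can move a result across 0.20; one reclassification or equal reclassification does not. The direction of any bias is unknown.

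**What to change.** 1. Add a named sensitivity analysis of the primary endpoint with non-completers as failures in every arm and all ITT patients in the denominator, shown beside the SAP-rule result. Define non-completer, which the protocol does not. List the change in SAP 4, with the date of the stopper review and whether it was blind to arm.
2. In SAP 6.6.1, give numerical limits for worsening and a number of weeks for reasonable duration. Say whether CRR or PRR, and which sample, defines a responder at the stop. Assign every stopper an outcome. State the rule 3 denominator for both the percentages and the models.
3. State the analysis rule for the exempt placebo patients. Also show a result that handles all stoppers after the unblinding by one rule, the same in every arm and defined by stop date.
4. Extend the planned listing to a by-arm summary of observed Week 52 spot UP/UC and serum creatinine, including stoppers at 42 weeks or later. Label it supportive: under Protocol 6.2.3.3 attendance was by invitation and stoppers could join another study, so data may be incomplete.

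**Cost.** SAP wording and a few tables. Some response rates will be lower under the failure rule. It can also favour BI 655064: if two approved placebo stoppers were in CRR, placebo falls from 7/15 to 5/15, that is 2/15 = 13 points. Both results must therefore be shown.
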